## **7.0 CLINICAL TRIAL MATERIAL MANAGEMENT**

This section contains information regarding all medication and materials provided directly by the sponsor, and/or sourced by other means, that are required by the study protocol, including important sections describing the management of clinical trial material.

### **7.1 Drugs / Substances / Devices**

Study immunotherapy solutions (noted above as PMA), composed of FDA approved allergens, will be supplied by the sponsor. PMA is prepared from a selection of FDA approved allergens and allergen mixtures listed in **Appendix E FDA Approved Allergens to be Used for Treatment**. Allergens used for skin prick testing are listed in **Appendix G Allergens used for skin prick testing**.

#### **7.1.1 Dosage Form, Preparation and Labeling**

The dosage (dilution) of PMA will be the same for all subjects and will begin with vial number #5 which will be prepared by serial five fold dilutions from the most concentrated vial (#1).

One PMA active treatment set will be prepared by compounding three separate concentrated vials (#1) each containing approximately 30 antigen mixtures (no more than about 75 total antigens each) and labeled mix A, B and C. No more than 0.9 ml of each manufacturer supplied stock material will be placed in a 100ml vial and brought to volume with diluent. Each of the #1 vials (A, B and C) will then be serially diluted 5 fold, several times approximately as follows:

	Mix A (Pollens)	Mix B (Indoor)	Mix C (Molds)	Exact Preparation
Vial #1	1:1	1:1	1:1	Described above
Vial #2	1:5	1:5	1:5	20ml Vial #1 + 85ml diluent
Vial #3	1:25	1:25	1:25	4ml Vial #1 + 85ml diluent
Vial #4	1:125	1:125	1:125	4ml Vial #2 + 85ml diluent
Vial #5	1:625	1:625	1:625	4ml Vial #3 + 85ml diluent

7.1.2 Vials #1-2 will have an expiration date of six months and dilutions #3-5 may be used for up to three months.

7.1.3 One placebo set will also be prepared in a similar manner using sterile saline and an equivalent amount of glycerin/phenol. Because up to 20% of patients receiving active treatment may notice local swelling and itch, histamine will be added to the stock placebo vials (vial 1) at a concentration of 50ug/ml (0.05mg/ml). Thus vial #2 will have a final concentration of 0.01mg/ml histamine. This is expected to elicit a mild itch in about 20% of control subjects based on experience.

Folic acid will also be added to the placebo vials to yield a slightly yellow color similar to the active treatment vials. Stock placebo (#1 vials) will contain 1mg/ml folic acid by adding 20ml of 5mg/ml folic acid to 80ml diluent. This will be further diluted 5 fold to yield (#2 vial) for a final concentration of 0.2mg/ml folic acid and so on.

The labeling of study PMA and placebo solutions will be undertaken by the compounding pharmacy of this investigation and undertaken in conjunction with the sponsor so that a double-blind study technique can be employed during the investigation. Each active and placebo vial set will be labeled randomly either set I or II. The set, mix letter, dilution, and use by date will also be included as shown by the example below. Only the pharmacy and sponsor will hold the treatment set randomization code. Recruited subjects will alternate between sets I and II.

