**Figure 5.a Schematic of Study Design**

## **5.2 Justification for Study Design, Dose, and Endpoints**

The question to be answered scientifically by this investigation is whether or not a new innovative, patented mixture of FDA approved antigens provides unequivocal superior clinical benefit in the symptomatic relief of individuals manifesting active SAR/PAR. Since extensive prior experience of managing patients with these medical conditions has demonstrated remarkable benefit from the immunotherapy technique within 3 to 6 weeks, the selection of study subjects and the overall study design can be scientifically justified.

The dose of immunotherapy, which will be administered sub-cutaneously bi-weekly for 8 weeks, will be the same for all subjects and will begin with vial number #5 which will be prepared by serial five fold dilutions from the most concentrated vial (#1).

The study sample size is based upon the results of prior immunotherapy investigations undertaken by the Investigators of this study and their colleagues in the Division of Allergy & Clinical Immunology, Johns Hopkins University School of Medicine. Efficacy for immunotherapy was

estimated to be 80% for treatment group and 30% for placebo. Using an error rate ( $\alpha$ ) of 0.05 and 80% Power we calculate a total sample size needed of 28 subjects. To account for drop off we will recruit up to 36 subjects.

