### **6.4 Criteria for Discontinuation or Withdrawal of a Subject**

The primary reason for discontinuation or withdrawal of the subject from the study or study medication should be recorded in the CRF using the following categories. For screen failure subjects, refer to Section 8.1.11.

1. Pretreatment event (PTE) or adverse event (AE). The subject has experienced a PTE or AE that requires early termination because continued participation imposes an unacceptable risk to the subject's health or the subject is unwilling to continue because of the PTE or AE.
2. Significant protocol deviation. The discovery postrandomization or after the first dose of study immunotherapy that the subject failed to meet protocol entry criteria or did not adhere to protocol requirements, and continued participation poses an unacceptable risk to the subject's health.
3. Lost to follow-up. The subject did not return to the clinic and attempts to contact the subject were unsuccessful. Attempts to contact the subject must be documented.
4. Voluntary withdrawal. The subject (or subject's legally acceptable representative) wishes to withdraw from the study. The reason for withdrawal, if provided, should be recorded in the

CRF. All attempts should be made to determine the underlying reason for the withdrawal and, where possible, the primary underlying reason should be recorded.

5. Study termination. The sponsor, IRB, or regulatory agency terminates the study.
6. Pregnancy. The subject is found to be pregnant.

Note: If the subject is found to be pregnant, the subject must be withdrawn immediately. The procedure is described in Section 8.1.10.

7. The investigator has determined that continued participation would pose an unacceptable risk to the subject.

Note: After the 30 minute wait period, subjects that develop local swelling at the site of the injection greater than 50mm diameter will have their next dose decreased by one step. Subjects having a Grade 1-2 systemic reaction will have their next injection decreased by two steps. Systemic reaction Grade 3 or more will require withdrawal from the study. Systemic reactions are defined by the World Allergy Organization anaphylaxis grading system (13).

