#### *7.1.4 Immunotherapy Dose and Regimen*

Recruited subjects alternate to be assigned either treatment set I or II (representing either placebo or active PMA treatment in a binded fashion). The assigned treatment set will remain for the duration of the study for each subject. On the day of an injection, 0.3ml from each of the appropriate vial set mix (A-C) will be combined in a sterile 5 ml bottle. Using a new sterile syringe, 0.15-0.60ml of the PMA solution or placebo will be removed for injection purposes according to the injection schedule (Appendix I). A sterile 27G ½ inch syringe will be used for administration. Immunotherapy will be administered bi-weekly in the study clinic for a total of eight consecutive weeks. Appendix I lists the precise immunotherapy injection schedule.

All patients are required to remain in the clinic under close observation by the study nurse for a period of 30 minutes following their injection. A physician is required to be present in the clinic at all times. In addition, one of the investigators must be present on campus and available by cell phone during scheduled treatment sessions. Emergency medications such as albuterol, oxygen, diphenhydramine, and at least two epi-pens will be readily available in the treatment area.

It is important to note that the maximum concentration of each individual allergen is quite low compared to more traditional immunotherapy regimens. The maximum PNU/ml (Protein Nitrogen Units) in vial #1 will be no more than about 180 PNU/ml per allergen (eg 0.9ml of 20,000 PNU/ml stock material into 100ml solution). In most cases the actual concentration of each stock allergen is much lower than 20,000 PNU/ml since the material may be provided as a mixture of several allergens. We would estimate therefore that subjects would receive no more than about 7.2 PNU of antigen contained in the highest injection (0.2ml Vial #2). Typically, allergens are administered via immunotherapy in a range of about 2000 PNU. Thus the dosage of each allergen is less than 0.36% of a typical dose administered in our clinics. The lower overall dosing scheme provided in this study would therefore be considered to be extremely safe with minimal adverse events.

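### The preparation volumes in Section 7.1.1 do not give the dilutions stated beside them; the starting vial comes out 26% too strong

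*Combined protocol and SAP*

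**What the plan says.** Section 5.2 and Section 7.1.1 of the protocol both describe serial five-fold dilution from vial #1, with every subject starting on vial #5. The table in 7.1.1 lists 1:5, 1:25, 1:125 and 1:625 for vials #2 to #5. Its last column, headed as the exact preparation, gives "20ml Vial #1 + 85ml diluent" for vial #2. Vial #3 is 4 ml of vial #1, vial #4 is 4 ml of vial #2, and vial #5 is 4 ml of vial #3, each with 85 ml of diluent; the vial #5 entry reads "4ml Vial #3 + 85ml diluent". The sentence introducing the table calls the scheme approximate.

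Other parts of the protocol use the nominal ratios:

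- Appendix H prints them beside each of the 16 injections.
- Section 7.1.4 puts the largest dose at about 7.2 PNU per allergen in 0.2 ml of vial #2.
- The placebo paragraph within 7.1.1 (numbered 7.1.3 there) starts from 0.05 mg/ml histamine in vial #1 and concludes "Thus vial #2 will have a final concentration of 0.01mg/ml histamine". Folic acid starts at 1 mg/ml and is diluted "for a final concentration of 0.2mg/ml folic acid and so on".
- The same paragraph makes the folic acid stock by "adding 20ml of 5mg/ml folic acid to 80ml diluent", which is a correct five-fold recipe.

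On dose reductions, Section 6.4 says that subjects with local swelling above 50 mm "will have their next dose decreased by one step"; a Grade 1-2 systemic reaction brings a two-step reduction. A step is not defined.

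**The concern.** This table is the compounding instruction for the investigational product. A pharmacist can follow the ratios or the volumes, but not both. Someone who follows the volumes makes vials whose strength differs from what the protocol states, and Appendix H escalates by vial number on the assumption that the ratios are right. Vials #3 to #5 may be used for only three months. If they are remade during the study and the conflict is resolved differently the second time, the same vial number could differ in strength between batches by up to 26%.

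The largest discrepancy is in the vial on which every subject starts. The errors also differ in sign and size, so the increases at vial changes are no longer equal, and some safety reductions under Section 6.4 could be smaller than Appendix H implies.

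**Working it through.** **Figures that use the stated ratios.** Successive five-fold dilution gives 5, 25, 125 and 625, as the table states. Taking 180 PNU/ml in vial #1 (Section 7.1.4), 180/5 × 0.2 = 7.2 PNU. Placebo vial #2: 0.05/5 = 0.01 mg/ml histamine and 1/5 = 0.2 mg/ml folic acid. All three figures therefore assume vial #2 is exactly 1:5.

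**Dilutions from the volumes in 7.1.1.** Dilution factor = (aliquot + diluent)/aliquot, multiplied by the factor of the source vial.

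| Vial | Calculation | Result | Stated | Strength relative to stated |
|---|---|---|---|---|
| #2 | 105/20 | 5.25 | 5 | 5/5.25 = 0.952 (-5%) |
| #3 | 89/4 | 22.25 | 25 | 25/22.25 = 1.124 (+12%) |
| #4 | 5.25 × 22.25 | 116.81 | 125 | 125/116.81 = 1.070 (+7%) |
| #5 | 22.25 × 22.25 | 495.06 | 625 | 625/495.06 = 1.262 (+26%) |

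**Alternative reading.** If 85 ml is the final volume: 85/20 = 4.25; 85/4 = 21.25; 4.25 × 21.25 = 90.3; 21.25 × 21.25 = 451.6. This does not match the stated series either.

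**Increase at vial changes.** Appendix H moves from 0.20 ml per mix of one vial to 0.05 ml per mix of the next, so the increase is (0.05/new factor)/(0.20/old factor).

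- #5 to #4: (0.05/116.81)/(0.20/495.06) = 1.06
- #4 to #3: (0.05/22.25)/(0.20/116.81) = 1.31
- #3 to #2: (0.05/5.25)/(0.20/22.25) = 1.06
- Nominal at each change: 5 × 0.05/0.20 = 1.25

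**Reductions under Section 6.4, taking a step as one Appendix H row.**

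- *Counted back from the dose that caused the reaction.* The nominal cut at a vial change is 1 - 1/1.25 = 20%. From the volumes it is 1 - 1/1.0595 = 5.6% at visits 6 and 14, and 1 - 1/1.3125 = 23.8% at visit 10. The other 12 of the 15 one-row cuts (visits 3 to 17) are within a vial and stay at 50%, 33.3% or 25%.
- *Counted back from the next scheduled dose.* After a reaction at visit 6, one step back from visit 7 repeats the visit 6 dose under either recipe. Two steps back gives the visit 5 dose, a cut of 5.6% instead of 20%. Visit 14 behaves the same way.

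**Total exposure, in ml of vial #1 equivalent per mix.**

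- Top dose: 0.20/5.25 = 0.0381 against 0.20/5 = 0.0400, or -4.8%.
- Cumulative: each vial contributes 0.05 + 0.10 + 0.15 + 0.20 = 0.50 ml. From the volumes, 0.50 × (1/495.06 + 1/116.81 + 1/22.25 + 1/5.25) = 0.1230. Nominal, 0.50 × (1/625 + 1/125 + 1/25 + 1/5) = 0.1248. The difference is -1.4%.

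**Placebo vial #2, if made with the same volumes.** 0.05/5.25 = 0.0095 mg/ml histamine; 1/5.25 = 0.19 mg/ml folic acid.

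**The case against.** The best defence is that the intent is plain, the scheme is called approximate, and the consequences are slight. The protocol sets no tolerance, so deciding how much discrepancy that word can cover is a matter of judgement. Vial #1 is itself loosely specified, with an upper limit on each stock volume and an approximate number of mixtures. Using the protocol's 180 PNU/ml, the first dose per allergen changes from 180/625 × 0.05 = 0.014 PNU to 180/495.06 × 0.05 = 0.018 PNU, against a typical dose that Section 7.1.4 puts at about 2000 PNU. Appendix H is already uneven: the within-vial increases are 2, 1.5 and 1.33, all larger than the worst vial-change increase of 1.31. The effect on Section 6.4 depends on a step that the protocol does not define, and the placebo figures are altered only if placebo is made with the same volumes.

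Most of this stands and limits the consequence. It does not reconcile the table. An approximate lead-in might cover 5% in vial #2, but not credibly 26% in the starting vial, under a column presented as exact and with errors in both directions. Clear intent shows which correction to make; it does not make the volumes right.

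**Conclusion.** The volumes and the stated dilutions in Section 7.1.1 contradict each other, and neither reading of 85 ml resolves it. This rests only on the table and simple dilution arithmetic. Discrepancies in strength run from -5% (vial #2) to +26% (vial #5).

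It should be corrected because it is a dosing instruction on which other sections rely, but its effect is limited. Every dose still rises, and sample size, power, the significance level and the analysis are untouched. The possible shrinkage of a safety reduction from 20% to 5.6% assumes that a step is one Appendix H row; the 20% is implied by that appendix rather than stated. The 180 PNU/ml assumption behind the 7.2 PNU bound was not verified, so nothing here confirms that bound.

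**What to change.** Change the preparation column, for active and placebo sets alike, to:

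- Vial #2: 20 ml vial #1 + 80 ml diluent (100/20 = 5)
- Vial #3: 4 ml vial #1 + 96 ml diluent (100/4 = 25)
- Vial #4: 4 ml vial #2 + 96 ml diluent (5 × 25 = 125)
- Vial #5: 4 ml vial #3 + 96 ml diluent (25 × 25 = 625)

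Appendix H and the placebo concentrations then need no change on this account.

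If the 85 ml volumes are what is actually compounded, restate the dilutions in 7.1.1 and Appendix H as 1:5.25, 1:22.25, 1:117 and 1:495, and placebo vial #2 as about 0.0095 mg/ml histamine and 0.19 mg/ml folic acid. That is the safer course if such vials are already in use, because changing the volumes would then alter the dose during the study. No change to the reduction rule in Section 6.4 is proposed here.

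The main correction costs four volumes in one table, plus any pharmacy worksheet that repeats them. Visits, sample size and analysis are unaffected.

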#### *7.1.3.2 Investigational immunotherapy*

The investigational immunotherapy used in this study protocol will be prepared by the Johns Hopkins University School of Medicine Division of Allergy and Clinical Immunology Laboratory (DACI) a national reference laboratory facility according to institutional policy and in accordance with USP 797 compounding standards. The allergens that will be used to constitute the study immunotherapy solutions will be directly shipped by nationally licensed corporate suppliers such as Greerlabs, Lenoir NC 28645-0800 and Allergy Laboratories, Oklahoma, City. All allergens used in the compounding of study immunotherapy solutions will be FDA approved materials.

Sterile saline, used for the production of the study placebo solution will be supplied by the vendor compounding pharmacy. A comparable amount of glycerin and phenol as well as histamine will be added to the placebo vials to mimic any local irritant reactions that may occur in the active treatment vials.

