**Table 9.a      Sponsor’s Medically Significant AE List**

Term	
Acute respiratory failure/acute respiratory distress syndrome	Hepatic necrosis
Torsade de pointes / ventricular fibrillation / ventricular tachycardia	Acute liver failure Anaphylactic shock

---

Malignant hypertension	Acute renal failure
Convulsive seizure	Pulmonary hypertension
Agranulocytosis	Pulmonary fibrosis
Aplastic anemia	Confirmed or suspected endotoxin shock
Toxic epidermal necrolysis/Stevens-Johnson syndrome	Confirmed or suspected transmission of infectious agent by a medicinal product
	Neuroleptic malignant syndrome / malignant hyperthermia
	Spontaneous abortion / stillbirth and fetal death

---

PTEs that fulfill 1 or more of the serious criteria above are also to be considered SAEs and should be reported and followed up in the same manner (see Sections 9.2.2 and 9.3).

It is important to note that out of more than 20,000 patients personally treated with the proprietary PMA allergen immunotherapy by [name] over the past 40 years, there HAS NEVER BEEN AN INCIDENT OF ANAPHYLAXIS OR SERIOUS SYSTEMIC REACTION attributed to the treatment. Epinephrine has never been required because of the treatment. Typical but uncommon side effects have included mild-moderate local swelling. These mild reactions occur at a rate of less than 20 percent.

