## STUDY DESIGN AND METHODS

### Study Design

This is a phase 2 proof of concept study. It is being undertaken to characterize and quantify the clinical difference in signs and symptoms that may evolve when subjects with active seasonal or perennial allergic rhinitis (SAR/PAR) are administered a sub-cutaneous form of immunotherapy in a double-blind, prospective, controlled six weeks study wherein a proprietary mixture of FDA approved allergens (PMA) is compared with saline placebo.

Randomization to active PMA versus placebo treatment is on a 1 to 1 ratio. A double-blind study design is used to minimize outcome bias. Randomization measures to minimize bias at study entry include computerized random assignment of treatment versus placebo vials.

Subjects who are receiving nasal steroids for their SAR/PAR at screening may continue in the screening process if they agree to discontinue their therapy and commence a 14-day wash-out period of their medication prior to receiving active/placebo immunotherapy. Potential study subjects who, at screening, are not on active treatment for their SAR/PAR and asthma may enter directly into the investigation provided they fulfil entry and exclusion criteria and screening testing requirements.

The population to be studied consists of male and female adults aged 18 years to 65 years who are actively manifesting SAR/PAR have a score of at least 28 on the mini-RQLQ and 6 on the TNSS scale.

[figure not shown]
The active treatment phase of the study will be for six weeks with a safety follow-up assessment at 30 days post-treatment. No interim analysis is planned.

The study immunotherapy that will be evaluated in this study is a new innovative proprietary mixture of FDA approved allergens which has been clinically developed and evaluated, during the past three decades, in some 20,000 patients by the inventor of the mixture (see 3.2). In clinical evaluation this patented antigen mixture has provided clinical symptomatic relief to patients with SAR/PAR in as brief a period as three administrations of immunotherapy injections and has an observed overall success rate of approximately 80 to 90 percent of such treated subjects.

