## **Secondary Outcomes**

1. Total nasal symptoms score (TNSS)- Comparison of the delta visit 2 to visit 17 (change in score) between both treatment groups I and II using an unpaired t test.
2. TNSS - Comparison of the delta visit 2 to visit 18 (change in score) between both treatment groups I and II using an unpaired t test.
3. Adverse Events - Adverse events (AEs) were to be spontaneously reported or elicited during open-ended questioning, examination, or evaluation of a patient. Comparison of the rates of adverse events between both treatment groups I and II will be evaluated using a one-tailed Fischer's exact test.

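### The adverse-event comparison pools local reactions although the placebo contains histamine meant to mimic them, so it cannot show local tolerability equal to saline

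*Combined protocol and SAP*

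**What the plan says.** Protocol 7.1.3 (printed under 7.1.1) gives the reason for the histamine: "Because up to 20% of patients receiving active treatment may notice local swelling and itch, histamine will be added to the stock placebo vials". The expected result in controls follows: "This is expected to elicit a mild itch in about 20% of control subjects based on experience". Section 7.1.3.2 states the aim: "histamine will be added to the placebo vials to mimic any local irritant reactions that may occur in the active treatment vials".

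Section 14.2 names slight swelling and discomfort at the injection site as the commonest side effect of allergen immunotherapy. The text after Table 9.a describes mild to moderate local swelling with PMA and adds: "These mild reactions occur at a rate of less than 20 percent".

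For the analysis, SAP secondary outcome 3 specifies "Comparison of the rates of adverse events between both treatment groups I and II" by a one-tailed Fisher's exact test, and protocol 12.1.3 lists the adverse-event rate as a secondary outcome tested between groups. Neither treats injection-site reactions separately. Section 12.1.4 tabulates treatment-emergent events by subject: overall, by system organ class and by preferred term. In the Study Design text of both protocol 5.1 and the SAP, PMA "is compared with saline placebo"; histamine is not mentioned there.

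**The concern.** A control that is made to react locally is a reasonable blinding device when the main endpoints are self-reported symptoms. It is a poor reference for local side effects. The rate of local reactions in controls is raised on purpose towards the rate expected on active treatment, and that control then serves as the comparator in the only planned between-arm test of overall adverse-event rates.

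A non-significant result could then be reported as adverse events no more frequent than on saline placebo. For local reactions the trial cannot support that statement, because no arm receives an inert injection. The overall count of subjects with at least one event has the same weakness, since a control whose only event is a histamine itch counts as a case. Safety is a central claim for PMA (protocol 3.2, 7.1.4 and 9.1.4), so the wording of this result matters.

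**Working it through.** **Inputs**
- Active arm: up to 20% with local swelling and itch (protocol 7.1.3).
- Control arm: about 20% with mild itch (protocol 7.1.3).
- Size: 36 subjects randomized 1:1, so 18 per arm (protocol 5.1). The calculated requirement of 28 (protocol 12.3) is 14 per arm and serves as a check on sensitivity.
- Test: one-tailed Fisher (SAP secondary outcome 3), with rejection at p ≤ 0.05. The SAP does not state the direction; I take it as an excess on PMA.
- Local-reaction rate on an inert injection: not in the documents. I assume 0% to 10%.

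The plan states no power for the adverse-event comparison, so there is no such figure to reproduce. Its histamine figure can be reproduced.

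**1. Histamine by vial.** The stock is 50 µg/ml. Vial #2 is 50 / 5 = 10 µg/ml = 0.01 mg/ml, which agrees with "Thus vial #2 will have a final concentration of 0.01mg/ml histamine". Further five-fold steps give 2, 0.4 and 0.08 µg/ml in vials #3, #4 and #5. Appendix H uses vial #2 at visits 14 to 17, which is 4 of 16 injections. The other 12 contain 5 to 125 times less histamine.

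**2. Expected counts.** Reading both figures as per-subject rates of any local reaction, 0.20 × 18 = 3.6 reactors are expected in each arm, a difference of 0. Because the active figure is a ceiling, the expected difference is at or below zero. Against an inert control at 0% to 5%, a 20% active rate would give a difference of 15 to 20 points.

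**3. Rejection threshold at 18 per arm.** With 0 control reactors, 4 active reactors give p = C(18,4)/C(36,4) = 3060/58905 = 0.052, and 5 give C(18,5)/C(36,5) = 8568/376992 = 0.023. Five are therefore needed. With 4 control reactors, 10 of 18 active reactors are needed.

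**4. Chance of flagging PMA.** This is the sum, over all pairs (a, b) with Fisher p ≤ 0.05, of Bin(a; n, active rate) × Bin(b; n, control rate). With a 0% control it reduces to P(X ≥ 5) for X ~ Bin(18, 0.20) = 1 − 0.716 = 0.284.

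| Active rate | Control rate | 18 per arm | 14 per arm |
|---|---|---|---|
| 20% | 20% (protocol) | 2.0% | 2.1% |
| 20% | 0% (assumed) | 28.4% | 30.2% |
| 20% | 2% (assumed) | 23.2% | 23.7% |
| 20% | 5% (assumed) | 16.6% | 16.3% |
| 20% | 10% (assumed) | 8.8% | 8.5% |
| 50% (assumed) | 20% (protocol) | 49.7% | 33.4% |
| 50% (assumed) | 5% (assumed) | 90.9% | 81.1% |

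In the first row, 2.0% is simply the test's false-positive rate.

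**5. Pooled total.** Suppose other events occur at a common rate r in both arms, independently of local reactions. The difference in subjects with at least one event is then (1 − r) × (active local rate − control local rate). It is zero at 20% v 20%, and (1 − r) × 20 points against a 0% control.

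**6. What remains estimable.** Incidence within the PMA arm does not depend on the control. For example, 4 of 18 is 22.2%, with an exact 95% interval of 6.4% to 47.6%.

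**The case against.** A reader might infer that PMA's commonest side effect is masked by construction, or that the adverse-event estimate is biased. The documents do not support either statement.

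- **Kind of reaction.** Controls are expected to have mild itch. The active reaction is swelling and itch, and sections 9.1.4 and 14.2 put swelling first. Mimicry is the stated aim, but nothing shows that the histamine reproduces swelling. Against this, a pooled test does not distinguish the two, and the single-diagnosis rule in 9.1.3 could merge them into one term.
- **Where the 20% applies.** The figure follows the vial #2 concentration and is not said to be per subject or per injection. This stands as a limit on size. It does not remove the point, because 12.1.4 counts a subject once, so a reaction at one late visit is enough.
- **Other safety outputs.** Section 12.1.4 reports incidence by arm and preferred term. Section 6.4 handles systemic reactions by grade and has a separate trigger for swelling over 50 mm, and the SAP compares epinephrine use. Nothing suggests that histamine hides these.
- **Validity.** PMA against histamine-containing placebo is a sound randomized contrast; it answers a different question from PMA against saline. Sections 7.1.3 and 7.1.3.2 disclose the histamine, and no section announces a claim against saline. The risk lies in how a null result is labelled and read.
- **Power.** Even a 0% control gives only 28.4% at a 20% active rate, so a null result was likely anyway. This argument weakens if PMA reacts more than expected: at an assumed 50%, the chance of detection is 49.7% instead of 90.9%. The same 49.7% shows that a large excess over histamine could still be found, so local reactions need not be barred from all testing.

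**Conclusion.** The concern holds for the between-arm contrast in local reactions and for any adverse-event total that contains them. Both are attenuated relative to an inert injection, and neither can support a claim that PMA is tolerated locally as well as saline. At the protocol's own rates the expected difference is about zero, and the test flags PMA in 2.0% of trials, against 28.4% or 16.6% with an inert control assumed at 0% or 5%. These figures assume 18 per arm, a one-tailed test for an excess on PMA, the two 20% figures read as per-subject rates, and control itch counted together with active swelling or itch. The inert rates and the 50% active rate are assumptions.

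The point does not extend to incidence in the PMA arm, graded systemic reactions or epinephrine use, and it is no reason to remove the histamine. It is a fault of analysis and labelling in a secondary outcome. It should be corrected, but it does not undermine the trial's design.

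**What to change.** Keep the histamine and amend the text before unblinding; a later decision on which events to set aside would not be credible.

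1. In SAP secondary outcome 3 and protocol 12.1.3 and 12.1.4, prespecify the main between-arm adverse-event comparison on systemic reactions (graded as in 6.4) and other non-local treatment-emergent events.
2. Report injection-site reactions separately for each arm, with exact 95% confidence intervals and with itch and swelling distinguished where recorded. Label any between-arm test of them as a comparison with histamine-containing placebo.
3. In protocol 5.1 and the SAP Study Design text, describe the control as histamine-containing saline placebo. State that no claim of local tolerability against an inert injection will be made.

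The cost is mainly wording. The main adverse-event test would no longer cover local reactions. The visit form (Appendix J) has only a free-text line for reactions, so itch and swelling may need separate entries.
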